At NU, the trial will be primarily implemented at the Robert H. Lurie Comprehensive Cancer Center. [name] is Director of the cancer center and will ensure that this trial is integrated into the cancer center clinics to facilitate recruitment. Cancer Center data indicate that ~6000 new patients/year are seen at the NU cancer center. Preliminary data ascertained for this proposal showed that, among 127 eligible cancer patients screened, 17 were smokers (13%) and 12 (71%) agreed to enroll in a smoking cessation program. Thus, based on ~6000 patients available for screening/year, we expect that ~780 will be smokers and ~546 will be interested in this study. Given the trial requirements and inclusion/exclusion criteria, we estimate that we can enroll ~10% of these patients for this trial (Martinez et al., 2009) or ~55 patients/year at NU (total sample at NU = 187 over 4 years).

Both PENN and NU will supplement recruitment with referrals from physicians and other cancer care providers at various cancer treatment centers within the Philadelphia and Chicago metropolitan areas.

Based on our extended therapy and bupropion trial with cancer patients ([name] et al., 2010a, 2010b), we expect that <20% of participants will withdraw from the trial and ~70% of participants will complete follow-up evaluations, which will exceed rates in varenicline trials (Jorenby et al., 2006). As is advised in smoking cessation trials (Hughes et al., 2003), intent-to-treat will be used for primary analyses, with missing outcome data coded as smokers (even due to death).

3. Key Inclusion Criteria

Eligible subjects will be males and females:

1. 18 years of age or older who self-report smoking at least 5 cigarettes per week, almost every week (menthol and non-menthol) on average, for the last 6 months.
2. Who have been diagnosed with a primary or secondary cancer (all sites) or have experienced a recurrence of a previously diagnosed cancer within the past 5 years. Those diagnosed >5 years ago without remission will also be eligible.
3. With a Karnofsky Score of ≥ 50 or ECOG Performance Status score of ≤ 2 within 6 months of enrollment.
4. Able to use varenicline safely, based on a medical evaluation including medical history and physical examination, and psychiatric evaluation.
5. Residing in the geographic area for at least 12 months.

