Smoking status is assessed using the timeline follow-back method (Brown et al., 1998) as done previously (Lerman et al., 2004; [name] et al., 2010b) and by using breath CO to verify self-report. Participants are considered abstinent if they self-report abstinence (not even a puff of a cigarette) for >7 days prior to the Week 24 and 52 assessment and have a breath CO of <10ppm at the time-point (SRNT, 2002; Hughes et al., 2003). As per convention, participants are assumed to be smoking if they self-report to be smoking at the time-point, cannot be reached to provide data at the time-point, fail to provide a breath sample at the time-point, or provide a breath sample at the time-point that is >10ppm (SRNT, 2002).

Cessation/Smoking Rate: Daily smoking (presence and rate) will be assessed at each visit after Intake Session with the well validated timeline followback method (TLFB). These data can be used to assess

the timing and rates of lapses (smoking episodes not lasting 7 days), recovery events (return to abstinence), and relapse events, as well as to monitor changes in smoking rates (i.e., # cigarettes/day). These data will also be used to compute and assess secondary measures of smoking cessation (e.g., continuous and prolonged abstinence).

Carbon Monoxide (CO) Test: Carbon monoxide will be measured at each in-person visit to confirm smoking status.

Other Smoking Measures (secondary)

As per recommendations (Hughes et al., 2003), we will also assess: prolonged abstinence to Weeks 12, 24, and 52 (relapse is 7 consecutive days of self-reported smoking, after a 2-week grace period), continuous abstinence at Weeks 12, 24, and 52 (no smoking between the quit day and follow-up), time to 7-day relapse (no grace period), smoking rate, and lapse (smoking episodes < 7 days) and recovery (return to 24-hour abstinence) events.

Quality of Life (QOL)

The Short-Form Health Survey (SF-12) will assess QOL (Ware et al., 1996). This scale yields physical and mental subscales, has been used to assess cancer patient QOL (McCorkle et al., 2009), has demonstrated validity and reliability (Gandek et al., 1998), and has been used in smoking cessation trials with cancer patients ([name] et al., 2010a). The SF-12 will be administered at all visits following the Intake Session.

2. Statistical Analysis

Power

Power is provided for the primary aims since the exploratory aim is hypothesis generating. All comparisons are 2-sided.

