Aim 1: The primary analysis is a comparison in Week 24 and Week 52 point prevalence quit rates between standard and extended therapy. For the week 24 comparison, we based our sample size on the expectation that the quit rate in the standard arm would be equal to the Week 24 quit rates reported in past clinical trials of varenicline for participants who received 12 weeks of treatment (i.e., 33%; Gonzales et al., 2006). We also expect to see at least the same effect on week 24 quit rates here as we saw in our past extended treatment trial (i.e., an OR of 1.81 or a difference of ~14%; [name] et al., 2010b). Thus, we have 80% power (alpha .05) with a sample of 374 if the difference between treatment arms in Week 24 quit rates is 14% (i.e., Week 24 quit rates for extended therapy is 47%). For the Week 52 comparison, we can expect a Week 52 quit rate for the extended arm of 56% (Tonstad et al., 2006), vs. 28% for standard treatment (Gonzales et al., 2006), for which we have 99% power (alpha = .05) with n = 374; we are powered to detect a difference at Week 52 of 14% if the present study yields a smaller effect than expected based on past studies.

Aim 2: The primary analysis is a comparison in Week 24 and Week 52 differences in QOL and severe side effects. For QOL, we have 80% power to detect a mean difference of 0.87 in physical QOL and a mean difference of 1.2 in mental QOL at any time-point, effects seen previously ([name] et al., 2010a). For side effects, the analyses will involve a test of non-inferiority since we cannot use standard statistical tests and conclude that a non-significant comparison means that the treatments are equal (i.e., “the absence of evidence is not evidence of absence”). In our past bupropion study ([name] et al., 2010a), 95% of placebo and 88% of bupropion participants reported no severe side effects. Assuming a similar difference, we have 90% power to detect equivalence with a floor of 80%, or an extended group that is 15% < the standard group.

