Aim 3: The analyses will assess changes in affect and cognitive impairment as mediators of treatment arm effects at Week 24 and 52. These measures are continuous difference scores. Our sample of 374 is well above the minimum sample of 200 recommended for models of this size (Haduk, 1987; Boosma & Gabrielli, 1985). The mediation hypothesis will examine the proportion of treatment effect explained (Lin et al., 1997; Vittinghoff et al., 2009), and test with a z-score generated using the delta method. Our sample of 374 gives us 80% power to observe small effects in a 1-sample test ($\delta=0.20$) when testing at $\alpha=0.05$. There are two proposed mediating pathways between treatment and outcome, so our type-1 error will be corrected to 0.025. Our sample of 374 gives us 80% power to detect small to medium effects ($\delta=0.22$) for changes in the proposed mediators.

[figure not shown]
Data Analysis

[name] will oversee analyses. Preliminary analyses will assess sample characteristics by treatment with chi-square or logistic regression (e.g., gender, dependence, depression, disease site). These variables will also be examined for their relationship to completion of outcome assessments. Variables related to treatment arm and completion of follow-ups will be included as covariates in analyses of study aims. Compliance measures will be evaluated across treatment arms, and controlled for in primary analyses. Although we will use an intent-to-treat analysis as the primary method for evaluating study aims, we will conduct a completers only analysis of study aims and examine study aims with participants lost to follow-up due to death excluded as done previously ([name] et al., 2003).

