Aim 1: Compare standard varenicline treatment (12-weeks active then 12-weeks placebo) to extended varenicline treatment (24-weeks active) for treating nicotine dependence among cancer patients. The hypothesized effect of treatment arm (i.e., the difference in quit rates between subjects receiving standard or extended treatment) will be tested by a treatment arm term in a binomial family with logit link (logistic regression) model that possibly includes terms for covariates. Outcomes of the logistic regression analyses will be characterized by odds ratios (e.g., odds of quitting smoking) and 95% confidence intervals. Although quit-rates at the end of 24 and 52 weeks will represent our primary outcome variables, similar logistic regression analyses will be performed for other assessments of quit rates (e.g., quit rates at Weeks 12 and 26). This model will be used for measures of prolonged and continuous abstinence as well. In addition, as many participants will fail to become completely abstinent, the negative binomial family log link for count data will be used to examine the main effects of treatment arm on changes in smoking rate. Time to (recurrent) event models will be fitted using Cox regression, stratified by event sequence, as in [name] et al. (2010).

Aim 2: Assess effects of extended varenicline therapy on QOL and varenicline side effects. Repeated-measures MANOVA will examine differences across treatment arms in mental and physical QOL over the trial. Covariates will be included, such as medical treatment history. We will compare treatment arms in terms of the frequency of severe side effects (individual and total). Logistic regression will test against the lower boundary on percent reporting only mild-moderate (i.e., < severe) side effects. The hypothesis test for equivalence is whether the OR is out of the prescribed range for the difference between the treatment arms.

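### The Aim 2 quality-of-life test is a repeated-measures MANOVA with no rule for missing SF-12 scores, so as written it is in effect a completers-only analysis, at odds with the intent-to-treat principle

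*Combined protocol and SAP*

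**What the plan says.** - **Method** (Statistical Analysis, Data Analysis, Aim 2): "Repeated-measures MANOVA will examine differences across treatment arms in mental and physical QOL over the trial". Covariates such as medical treatment history are added. Nothing is said about missing scores.
- **Comparison of interest** (Statistical Analysis, Power, Aim 2): "The primary analysis is a comparison in Week 24 and Week 52 differences in QOL and severe side effects".
- **Power** (same paragraph): "we have 80% power to detect a mean difference of 0.87 in physical QOL and a mean difference of 1.2 in mental QOL", described as applying at any time-point. No SD, sample size or attrition allowance accompanies it.
- **Schedule** (Quality of Life section): "The SF-12 will be administered at all visits following the Intake Session". Table 2 makes that ten visits: Weeks 0, 1, 4, 8, 12, 14, 18, 24, 26 and 52.
- **Expected losses** (Accrual): "we expect that <20% of participants will withdraw from the trial and ~70% of participants will complete follow-up evaluations".
- **Missing-data rule** (Accrual): a participant with no outcome is counted as smoking, deaths included. No other rule appears.
- **Analysis principle** (Data Analysis, opening paragraph): "we will use an intent-to-treat analysis as the primary method for evaluating study aims". A completers-only analysis, and one leaving out participants lost through death, are listed as additions. Variables related to follow-up completion enter the models as covariates.

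**The concern.** A classical repeated-measures MANOVA works on one complete row of scores per participant. One absent SF-12 among ten removes that participant from every time-point, including visits where a score was obtained. A covariate for follow-up completion cannot bring back someone the procedure has already dropped.

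The smoking rule fills a gap in a yes/no abstinence outcome but produces no value for a continuous score. The complete-case default therefore decides who is analysed, and the main QOL analysis collapses into the completers-only analysis that the plan treats as supplementary.

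Three things are at stake. The arms would no longer be compared as randomised for an aim that carries its own hypothesis. Data already collected would be thrown away. An omnibus test over ten visits does not by itself estimate the Week 24 and Week 52 differences that the power section names. If withdrawal or death is related to QOL, or differs by arm once the treatments diverge on Day 85, the comparison could also be biased.

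**Working it through.** **Inputs.** Stated differences 0.87 (physical) and 1.2 (mental) with 80% power (Power, Aim 2). Two-sided tests (Power, opening lines). Total of 374 and alpha 0.05 are stated for Aim 1 ("we have 80% power (alpha .05) with a sample of 374") and are assumed here to carry over to QOL. Follow-up of 70% is from Accrual. Equal allocation, 187 per arm, is assumed.

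**1. The plan's figure.** The 80% cannot be reproduced independently, because neither SD nor n is given. Solving backwards, 80% power at two-sided 0.05 needs a difference of 1.960 + 0.842 = 2.80 standard errors:

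- SD = difference / (2.80 × √(2/187)) = difference / 0.290
- Physical: 0.87 / 0.290 = 3.00. Mental: 1.2 / 0.290 = 4.14.

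Both correspond to a standardised difference of 0.290. Had the 80% already been computed on 262 participants, the implied SDs would be 2.51 and 3.47. The document does not show which basis was used.

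**2. Power at one time-point with fewer participants, if 374 was the basis.** Power = Φ(2.80 × √fraction − 1.96).

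| Fraction analysed | Participants | Power |
|---|---|---|
| 100% | 374 | 80% |
| 80% | 299 | 71% |
| 70% | 262 | 65% |
| 60% | 224 | 58% |

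At 70%: 2.80 × √0.70 = 2.34, giving 65%. The differences detectable with 80% power grow by √(374/262) = 1.195: 0.87 becomes 1.04 and 1.2 becomes 1.43.

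**3. Extra loss from dropping incomplete rows.** The plan gives no per-visit rate. Assuming independent attendance at each of ten visits: 97% leaves 0.97¹⁰ = 74% complete (power 67%); 95% leaves 60% (58%); 90% leaves 35% (38%). These are illustrations only.

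**4. What a mixed model would recover.** Suppose 70% have the final score, everyone has k earlier scores, and the correlation between any two visits is ρ (all assumed). With R² = kρ² / (1 + (k−1)ρ), the variance relative to full data is (1 − R²)/0.70 + R².

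- ρ = 0.4, k = 2: R² = 0.23, ratio 1.33, power about 68%.
- ρ = 0.7, k = 9: R² = 0.67, ratio 1.14, power about 75%.

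So most of the fall from 80% to 65% is attrition, and the model recovers part of it.

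**5. Would a test averaged over all visits keep its power?** With 131 per arm, the SD of a ten-visit mean is √((1 + 9ρ)/10) in units of the single-visit SD. If the difference were 0.290 SD at every visit, power would be 93% at ρ = 0.4, 83% at 0.6, 78% at 0.7 and 69% at 0.9. But Weeks 0, 1, 4, 8 and 12 precede the Day 85 switch, and both arms take the same active drug until then. With no difference at five of ten visits, the average halves to 0.145 SD, and power is about 41% at ρ = 0.4 and 23% at ρ = 0.9.

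**The case against.** The best defence has five parts.

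- **Dropping incomplete cases is a default of the method, not a rule in the plan.** True. This is an unspecified missing-data method in tension with intent-to-treat, not an announced exclusion. But no alternative is named, so the default would govern.
- **The power loss is conditional.** A reader might infer that the QOL comparison is simply not 80% powered. The documents do not support that: n and SD are absent, and an allowance for attrition cannot be ruled out. A reader might also blame the whole fall to 65% on MANOVA; step 4 shows that most of it is attrition. The test averaged over visits is no rescue, because it depends on an effect before the arms differ and because the stated power is for any single time-point.
- **The 70% refers to follow-up evaluations, not to ten complete SF-12s.** A reader might infer that at least 30% are excluded. That figure is not given, and the true share could lie on either side of it.
- **Nothing says who will be missing.** A reader might infer that the sickest patients are excluded. Deaths are anticipated, so under-representation of those who withdraw or die is plausible, but the documents do not establish it. Sessions may be completed by telephone (note above Table 2), and covariates related to completion are planned. Both help, and neither restores a dropped participant.
- **QOL is not the primary outcome.** Outcome Assessments lists it among the others. It still carries a stated hypothesis and a power claim under Aim 2.

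**Conclusion.** The point holds in this form: the named method, with no rule for missing SF-12 scores, yields in effect a completers-only analysis where the plan promises intent-to-treat, and it does not directly deliver the Week 24 and Week 52 contrasts. That follows from the plan's text and the standard behaviour of repeated-measures MANOVA, without any assumption about who drops out.

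The size is conditional. If the 80% assumes all 374, data on about 262 at a time-point give about 65% power, with detectable differences of about 1.04 (physical) and 1.43 (mental). Any further loss from deleting incomplete rows depends on a missed-visit rate that the plan does not state. The direction and size of any bias cannot be determined from the documents. The trial's abstinence analysis is unaffected. The plan should be changed, because a better analysis is available from the same data.

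**What to change.** - Replace the MANOVA with a likelihood-based mixed model for repeated measures, fitted separately to the physical and mental scores, with arm, visit, arm-by-visit and the Week 0 score as covariate.
- Include every SF-12 obtained, also those taken after study drug is stopped. Report the arm contrasts at Weeks 24 and 52.
- State how deaths are handled in the QOL comparison. The planned analysis leaving out deaths can stay as a supplement.
- Add a sensitivity analysis for data missing not at random, for example imputed scores shifted downward by arm over a stated range. The mixed model is valid only if missingness is explained by the observed data, so it does not settle the bias question alone.
- Restate the QOL power with its SD, sample size and expected attrition at Weeks 24 and 52.

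The cost is plan wording, somewhat more analysis in standard software, and probably a less favourable stated power. No new data are needed.

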8. Complete baseline paper and pencil measures to assess 1) background variables that may serve as covariates and will allow for assessment of external validity (e.g., smoking history, demographics); 2) mediators (e.g., affect), 3) moderators (e.g., disease-related information), and 4) baseline smoking behavior.

If eligible at this point, subjects will be scheduled for the first treatment session (Week 0). There must be no more than 60 days between the Intake Session and the first treatment session (Week 0, Pre-Quit). If 60 days elapses between these sessions, all intake measures must be re-administered and evaluated by the study physician before Pre-Quit can occur (both sessions may be completed on the same day pending study physician approval by phone).

Behavioral Counseling (Week 0-Week 18).

All subjects will receive manual-based counseling from a counselor trained and supervised by [name]. The counseling protocol is based on PHS guidelines for smoking cessation treatment (Fiore et al., 2008), used in our past studies with cancer patients ([name] et al., 2010a) and in our ongoing cessation trial at NU (R01 DA025078). Counseling is included given its efficacy at helping smokers quit (Fiore et al., 2008) and to increase study retention. Counseling is provided to both treatment arms through Week 18 to equate for time and attention across arms and since this method was used in varenicline clinical trials (Gonzales et al., 2006) and in our extended therapy trial ([name] et al., 2010b). In-person counseling was selected for most sessions to ensure adequate monitoring of participant safety and adherence throughout the trial. Sessions are arranged at convenient times for the participants, including evenings.

Pre-Quit Session (Week 0): The counseling program begins at Week 0 with a 1-hour in-person "pre-quit" counseling session to prepare for the target quit day. This session focuses on reviewing participant's history and experience with quitting, beliefs about smoking and quitting, and perceived barriers to cessation, and

initiates a quitting plan involving identifying smoking triggers and identifying strategies to increase the chance for success, including relying on social support and altering behaviors associated with smoking. Medication is dispensed at this session and will begin following the session.

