Quit Day Session (Week 1): At Week 1, participants will receive a 30-minute in-person “quit-day” session to review the initial quit attempt, identify potential reasons for relapse, and review a plan for avoiding tempting situations.

Relapse Prevention Sessions (Weeks 4, 8, 12, 14, and 18): Participants will then receive 5 additional 20-minute sessions (in-person or over the telephone) at Weeks 4, 8, 12, 14, and 18 which either reinforce success and review the quit plan or reestablish a quit date and restart the cessation process. The sessions are designed to enhance awareness of the harmful effects of smoking, assist the person in developing skills to quit and avoid relapse, and instruct the smoker on varenicline use. All sessions may be audio-taped and a random 15% of sessions are assessed for protocol adherence. The counselor is blind to randomization.

Varenicline or Placebo Treatment (Weeks 0-24).

Varenicline will be used in accordance with FDA approved labeling: Day 1-Day 3 (0.5mg once daily); Day 4-Day 7 (0.5mg twice daily); and Day 8-Day 84 (1.0mg twice daily). On Day 85, participants randomized to standard therapy will be given placebo pills (resembling the 1.0mg pills), while extended therapy participants will continue with active varenicline (1.0mg twice daily). Participants will take this medication until Day 168. Extended therapy was defined as 24 weeks to be consistent with previous trials ([name] et al., 2010b).

If a participant is not able to attend a medication pick up visit (Week 4 or Week 12), the session will be completed over the phone and, if eligible, one week of study medication will be mailed to the participant from the research pharmacy. Participants will need to schedule a brief appointment in-center to complete a blood pressure evaluation before additional study medication is dispensed (session blood pressure procedures apply). If the Week 4 or Week 12 assessments cannot be completed over the phone within the session window, participants will be invited to a brief in-center appointment for a side effects assessment and blood pressure evaluation before additional study medication is dispensed (session side effects and blood pressure procedures apply).

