Participants will also be told that varenicline may impair their ability to perform tasks requiring judgment or motor and cognitive skills and that they should proceed with caution in this regard until they are certain that varenicline does not affect their performance. Participants will be told that varenicline may be associated with somnambulism (sleep walking) that may result in harmful behavior to self, others, or property, and if they notice such behaviors that they should discontinue varenicline and notify the study staff after seeing their medical provider. Participants will also be advised that Chantix may affect their response to alcohol including lower alcohol tolerance, aggressive behavior, or impaired memory following consumption of alcohol. Participants will be instructed to minimize alcohol intake (no more than 3 drinks per occasion or within a 24-hour time period) while taking varenicline. Participants will be advised to inform the study staff if they are taking or plan to take any prescription or over-the-counter drugs. Women will be advised to notify the study staff if they become or intend to become pregnant during the study period. The research team has extensive prior experience conducting smoking cessation trials with varenicline.

Withdrawal. Many individuals who quit tobacco use exhibit a pattern of symptoms associated with withdrawal from tobacco use. These symptoms can include: sadness and anxiety, irritability, difficulty concentrating, anger, appetite change and weight gain, insomnia, and decreased heart rate. Eliminating the risk for these would not be possible, although in most cases these events are short-lived and have low intensity, lasting for 1-2 weeks. Use of varenicline (by all participants for the first 12 weeks of the study) will also minimize the severity of withdrawal symptoms and behavioral counseling will also offer strategies for reducing withdrawal. The study personnel will be trained to recognize these symptoms and educate the participants about them (e.g., their duration, methods for reducing them).

Blood Draws. Blood draws may result in bruising and/or slight bleeding at the needle site. This is rare and happens infrequently. Occasionally, blood drawing results in a feeling of faintness. This too is rare. A trained professional will draw blood, so the chances of these discomforts are minimal. Procedures are in place to ensure that PHI is not linked with the results of this research.

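### The quality-of-life model in Aim 2 does not identify the primary Week 24 and Week 52 differences and does not name the pre-drug SF-12 score as a covariate

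*Combined protocol and SAP*

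**What the plan says.** Under Power, Aim 2: "The primary analysis is a comparison in Week 24 and Week 52 differences in QOL and severe side effects". The same paragraph claims 80% power for a mean difference of 0.87 (physical) and 1.2 (mental) at any single time-point.

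Under Data Analysis, Aim 2, the whole QOL method is: "Repeated-measures MANOVA will examine differences across treatment arms in mental and physical QOL over the trial". The next sentence is "Covariates will be included, such as medical treatment history". The opening paragraph of Data Analysis adds a general rule: "Variables related to treatment arm and completion of follow-ups will be included as covariates in analyses of study aims".

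On measurement, the Quality of Life paragraph says "The SF-12 will be administered at all visits following the Intake Session". Table 2 shows ten such visits: Weeks 0, 1, 4, 8, 12, 14, 18, 24, 26 and 52. Week 0 precedes drug, since the Pre-Quit Session paragraph says "Medication is dispensed at this session and will begin following the session". The dosing text has both arms on the same active drug through Day 84, and the standard arm changes to placebo on Day 85.

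**The concern.** The two parts of the statistical section do not meet. One names two time-points as primary. The other names a multivariate model over the trial without saying which visits are responses, whether arm or arm-by-time is tested, or how a Week 24 or Week 52 difference is obtained. An analyst could defend several quite different analyses from this text after seeing the data.

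Baseline SF-12 is also absent. The QOL covariates are given by one example, medical treatment history. The general rule selects variables from the data, so it does not guarantee that the Week 0 score enters. Elsewhere the plan does use baseline: mediators are change scores, and side effects are tracked as change from Pre-Quit. No equivalent is defined for QOL.

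At stake are the precision of a hypothesised Aim 2 benefit, protection against chance baseline imbalance, and a primary QOL estimate that is fixed in advance.

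**Working it through.** **Inputs from the plan.** N = 374; two-sided tests; alpha 0.05 (stated for Aim 1, taken to apply here); mean differences 0.87 and 1.2 with 80% power; ten SF-12 visits, of which five (Weeks 0, 1, 4, 8, 12) nominally precede Day 85.

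**Assumptions.** 187 per arm; between-visit correlation ρ of 0.3, 0.5 or 0.7 with compound symmetry; complete data. For the multi-visit tests, the effect is also taken as constant over Weeks 14-52.

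**The plan's own figure.** No SD is given, so the 80% can only be inverted. The standardised effect is d = (1.960 + 0.842) × √(2/187) = 0.290. This implies an SD of 0.87/0.290 = 3.00 for the physical scale and 1.2/0.290 = 4.14 for the mental scale. The stated power is neither confirmed nor refuted. Below, power = Φ(signal − 1.960), and the unadjusted single-visit signal is 2.802.

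**Single visit (Week 24 or 52) adjusted for Week 0.** Residual variance is multiplied by 1 − ρ², a fall of 9%, 25% or 51%. Signal = 2.802/√(1 − ρ²):
- ρ = 0.3: 2.802/0.954 = 2.937, power 83.6%
- ρ = 0.5: 2.802/0.866 = 3.235, power 89.9%
- ρ = 0.7: 2.802/0.714 = 3.923, power 97.5%

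**Arm main effect over all ten visits.** With an expected effect of zero at five visits and d at five, the averaged effect is d/2 (0.87 becomes 0.435; 1.2 becomes 0.60). The variance of a ten-visit mean is (1 + 9ρ)/10 in SD² units. Signal = 1.401/√((1 + 9ρ)/10):
- ρ = 0.3: 1.401/0.608 = 2.303, power 63.4%
- ρ = 0.5: 1.401/0.742 = 1.889, power 47.2%
- ρ = 0.7: 1.401/0.854 = 1.640, power 37.4%

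**Arm-by-time test in the same model.** Noncentral F with 9 and 364 df. The noncentrality is (374/4) × 2.5 × d²/(1 − ρ) = 19.6/(1 − ρ), that is 28.0, 39.2 and 65.4.

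| ρ | One visit, unadjusted | One visit, Week 0 adjusted | Ten-visit arm main effect | Arm-by-time |
|---|---|---|---|---|
| 0.3 | 80% | 83.6% | 63.4% | 97.7% |
| 0.5 | 80% | 89.9% | 47.2% | 99.8% |
| 0.7 | 80% | 97.5% | 37.4% | >99.9% |

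**Sensitivity.** The Accrual section expects about 70% to complete follow-up, or about 131 per arm. The unadjusted single-visit power is then 65%, and the adjusted power is 69%, 77% or 91%.

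**The case against.** A reader might infer that the plan enters Weeks 0-12 as outcomes, averages the arm effect over them, and so is likely to miss a real benefit. The documents do not support that. The MANOVA sentence names neither visits nor test term. The Power section puts the primary comparison at two weeks that both follow Day 85, where there are no null visits to average over. If the test were arm-by-time, power at the planned effect would be 98-100%.

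Nor are early visits harmful in themselves. Under the same assumptions, the post-Day-84 mean minus the pre-Day-85 mean has variance 0.4(1 − ρ), or 0.28, 0.20 and 0.12. The post-Day-84 mean adjusted for Week 0 has (1 + 4ρ)/5 − ρ², or 0.35, 0.35 and 0.27. Dilution therefore comes from one choice of test term, and such a contrast would also remove chance baseline differences.

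The covariate wording is open-ended too, so Week 0 SF-12 is not excluded.

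All of this stands. It does not close the gap. Arm-by-time is an omnibus test that does not itself give the Week 24 or Week 52 difference, and a contrast averaged over five visits estimates something other than the two named time-points. Not excluding the baseline score is weaker than prespecifying it.

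**Conclusion.** The point holds as under-specification plus a forgone baseline adjustment. The plan names Week 24 and Week 52 as primary for QOL but gives no model term that yields those estimates, and it does not commit to adjusting for the Week 0 SF-12.

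For a single-visit comparison, the cost of leaving out baseline is about 4, 10 or 18 percentage points of power at correlations of 0.3, 0.5 or 0.7. The halved effect, with 37-63% power, applies only if the ten-visit arm main effect were chosen; the text permits that but does not state it.

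The sizes rest on the assumed correlation, compound symmetry, equal allocation and complete data, and the multi-visit figures also on a constant effect after Day 84. The zero effect before Day 85 is an expectation at nominal visit times: a Week 12 visit within its one-week window could fall after the switch. This is an inexpensive improvement to a secondary aim and does not show that the planned analysis would fail.

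**What to change.** Replace the MANOVA sentence with a specification along these lines. For each SF-12 scale (physical and mental), fit a repeated-measures model to the post-Day-84 visits (Weeks 14, 18, 24, 26 and 52), with arm, visit, arm-by-visit and the Week 0 SF-12 score of that scale as covariate. Report the adjusted arm differences at Week 24 and Week 52, with 95% confidence intervals, as the primary QOL result. List any further covariates by name.

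This brings Data Analysis into line with Power. It costs only a change of wording: every score is already scheduled, and no visit, sample size or procedure changes. Stating the SD and the correlation assumed for the 80% claim would let the power be checked.
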